Days from index to first ICANS event	Outcome	MDV	Time in days from index date to first ICANS event (continuous)	CRS/ICANS follow-up assessment period
Cytopenia occurrence ¹	Outcome	MDV	Disease code or labs value for cytopenias occurrences (Yes/No): 
 Anemia Leukopenia Lymphopenia Neutropenia Thrombocytopenia Number and proportion of patients with a health claim code for each cytopenia will also be reported. Incidence and prevalence will be reported, see Section 9.7.2 for additional details.	SUD period
Days from index to first cytopenia	Outcome	MDV	Time in days from index date to first cytopenia (continuous)	SUD period

090177e1a4a71ff1\Approved\Approved On: 05-Nov-2025 14:15 (GMT)

Abbreviations: CRS: cytokine release syndrome; ICANS: Immune effector Cell Associated Neurotoxicity Syndrome; SUD: step-up dosing.

Notes:

1. Variable will be measured as incident and prevalent. Incident cases have a 30-day washout period applied.

Table 8. Variables for Outcomes (Objective 6 - Infections)

Variable	Role	Data Source	Operational Definition	
			Definition	Assessment Period(s)
Infection occurrences ¹	Outcome	MDV	Disease code for infections; the list of infections of interest will be outlined in the SAP (Yes/No) Incidence and prevalence will be reported, see Section 9.7.2 for additional details.	Follow-up period
Days from index to infection	Outcome	MDV	Time in days from index date to first infection (continuous)	Follow-up period
Days between infections	Outcome	MDV	Days between infection claims (continuous) For patients with ≥ 2 disease code for infections listed in the SAP during the time period	Follow-up period

Variable	Role	Data Source	Operational Definition	
			Definition	Assessment Period(s)
Antibiotics	Outcome	MDV	Health claim code for antibiotic treatment (Yes/No)	Follow-up period
Antivirals	Outcome	MDV	Health claim code for antiviral treatment (Yes/No)	Follow-up period
Antifungals	Outcome	MDV	Health claim code for antifungal treatment (Yes/No)	Follow-up period

Notes:

1. Variable will be measured as incident and prevalent. Incident cases have a 60-day washout period applied.

Table 9. Variables for Outcomes (Exploratory Objective 1 – Supportive Medications)

Variable	Role	Data Source	Operational Definition	
			Definition	Assessment Period(s)
Dexamethasone	Outcome	MDV	Health claim code for dexamethasone (Yes/No)	SUD period
Diphenhydramine	Outcome	MDV	Health claim code for diphenhydramine (Yes/No)	SUD period
Acetaminophen	Outcome	MDV	Health claim code for acetaminophen (Yes/No)	SUD period
Tocilizumab	Outcome	MDV	Health claim code for tocilizumab (Yes/No)	SUD period

Variable	Role	Data Source	Operational Definition	
			Definition	Assessment Period(s)
IVIG	Outcome	MDV	Health claim code for IVIG (Yes/No)	IVIG follow-up assessment period

Abbreviations: IVIG: intravenous immunoglobulin; SUD: step-up dosing.

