- **Data Analysis:** Descriptive statistics will be used for all objectives, and no hypothesis testing will be conducted. Incidence and prevalence calculations will be conducted.

- **Milestones:** The study will be registered in the HMA-EMA Catalogues of RWD studies on July 14, 2025, followed with data collection commencing on July 15, 2025. An interim study analysis is scheduled for release on September 30, 2025. Data collection will conclude on June 30, 2026, followed by the final study report on November 30, 2026.

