8. RESEARCH QUESTIONS AND OBJECTIVES

Research Question: What are the characteristics of adult patients with MM who initiate elranatamab in Japan, and the SUD process, treatment patterns, HCRU, and safety associated with elranatamab administration?

The following objectives will be assessed among patients with MM receiving elranatamab:

Primary objectives:

- Objective 1: To describe patients with MM initiating elranatamab, including demographics, treatment and medical history.
- Objective 2: To describe and characterize elranatamab utilization, including timing, administration and dosing, during the follow-up period, including the step-up dosing (SUD) period.

Secondary objectives:

- Objective 3: To describe HCRU and costs associated with elranatamab usage during the follow-up period, including the SUD period.
- Objective 4: To describe the use of other treatments for MM including supportive therapy during the follow-up period.
- Objective 5: To describe incidence and prevalence of cytokine release syndrome (CRS), immune effector cell associated neurotoxicity syndrome (ICANS), and cytopenias during the SUD period.
- Objective 6: To describe infection incidence and prevalence during the follow-up period.

Exploratory objectives:

- Exploratory Objective 1: To describe the use of supportive medications during the SUD period and administration of IVIG within the 30-day post-index period.

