9. RESEARCH METHODS

9.1. Study Design

This retrospective cohort study will assess the demographics, clinical history, SUD process, HCRU, and safety of elranatamab in MM patients with an elranatamab hospital claim. De-identified data from the Japan Medical Data Vision (MDV) will be used.

[figure not shown]
A retrospective cohort design was chosen because it allows for efficient use of existing RW data to evaluate treatment patterns and outcomes in a newly approved therapy, without the need for prospective data collection. This design is well-suited for descriptive analyses and enables timely insights into the early use of elranatamab in a RW setting.

The primary endpoints include patient demographics, clinical characteristics, and treatment patterns. Secondary endpoints include HCRU and safety outcomes. No formal measures of effect will be calculated. All analysis will be descriptive, with no a priori hypotheses or statistical comparisons between exposure groups.

The study population will be comprised of individuals aged 18 and older who initiated elranatamab between March 26, 2024, the PMDA approval date for elranatamab, and the end of data availability. The study period will be from the start of data availability, April 2008, to the end of data availability in MDV. The study period will remain the same for all study objectives. The patient baseline period will be from MM diagnosis to the start of the index treatment. The patient index date will be determined as the date of first hospital claim with an administration of elranatamab. The follow-up period will be defined as the period between the index date and the end of the hospital claim of the last elranatamab administration

inclusive. The SUD period will be defined as the period between the date of the first 44mg/1.1mL vial and the first 76mg/1.9mL vial of elranatamab, see more details in Section 9.2 and 9.3.1. Figure 1

Figure 1. Study design

Abbreviations: CCI: Charlson Comorbidity Index; HCRU: Health Care Resource Utilization; MM: multiple myeloma; SUD: Step-up dosing;

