Duration of treatment, patient level	Outcome	MDV	Days between first and last treatment administration for elranatamab (continuous)	Follow-up period
Duration of treatment, claim level	Outcome	MDV	Total calendar duration of elranatamb observation in days, and the date of the first observed elrantatamab claim	Follow-up period
Only 44mg/1.1mL vials [Summary statistic]	Outcome	MDV	Number of patients with only 44mg/1.1mL vials during the time period (yes/no)	Follow-up period
Only 76mg/1.9mL vials [Summary statistic]	Outcome	MDV	Number of patients with only 76mg/1.9mL vials during the time period (yes/no)	Follow-up period
Relative Administration Intensity (RAI) [Summary statistic]	Outcome	MDV	Ratio of the elranatamab administrations received divided by the expected number of administrations according to the Japan elranatamab label See Section 9.7.4 for more details	Follow-up period

Abbreviations: mL: millilitre; mg: milligram; RAI: Relative Administration Intensity; SUD: step-up dosing.

Table 5. Variables for Outcomes (Objective 3 – HCRU and Costs)

090177e1a4a71ff1\Approved\Approved On: 05-Nov-2025 14:15 (GMT)

Variable	Role	Data Source	Operational Definition	
			Definition	Assessment Period(s)
IP claim [Summary statistic]	Outcome	MDV	Number of patients with ≥ 1 all-cause IP claim (yes/no)	HCRU baseline period SUD period Follow-up period (overall only)
			Number of all-cause IP claims PPPM. Reported for all patients and for patients with ≥ 1 all-cause IP claim.	HCRU baseline period Follow-up period (overall only)
			Number of all-cause IP claims PPPD. Reported for all patients and for patients with ≥ 1 all-cause IP claim.	SUD period
OP claim [Summary statistic]	Outcome	MDV	Number of patients with ≥ 1 all-cause OP claim (yes/no)	HCRU baseline period SUD period Follow-up period (overall only)
			Number of all-cause OP claims PPPM. Reported for all patients and for patients with ≥ 1 all-cause OP claim.	HCRU baseline period Follow-up period (overall only)
			Number of all-cause OP claims PPPD. Reported for all patients and for patients with ≥ 1 all-cause OP claim.	SUD period

090177e1a4a71ff1\Approved\Approved On: 05-Nov-2025 14:15 (GMT)

Variable	Role	Data Source	Operational Definition	
			Definition	Assessment Period(s)
ED claim [Summary statistic]	Outcome	MDV	Number of patients with ≥ 1 all-cause ED claim (yes/no)	HCRU baseline period SUD period Follow-up period (overall only)

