9.5. Study Size

The study sample will be identified from secondary data from Japanese hospitals that has already been collected. As the MDV database does not include all Japanese hospitals, the sample will be a convenience sample. The most recent data cut available from MDV will be used for the report. All patients who meet the inclusion/exclusion criteria defined in [Section 9.2](#) will be included in the analyses.

This is a descriptive study with no a priori hypotheses; therefore, formal sample size calculations are not applicable. However, to provide an indication of the expected sample size, the February 2025 data cut, MDV included 128 patients that had at least one hospital claim for elranatamab.

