9.7.1. Descriptive Analysis

Dichotomous and categorical variables will be summarized by the number and percentage of patients in each category. Continuous variables will be described using mean, standard deviation (SD), median, interquartile range (IQR), minimum, and maximum. If applicable, the frequency and percentage of patients with missing data for each variable will be described. For reporting conventions, mean, median, and SD will be rounded to 1 decimal place. Percentages will be rounded to 1 decimal place.

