9.7.3. Relative Administration Intensity

RAI will be calculated as the cumulative frequency of administration received over the expected number of administrations. Since response is needed to determine if switching to bi-weekly doses is appropriate and is not available in MDV, two schedule definitions will be used to estimate the expected number of administration to calculate RAI (Table 10. Dosing Schedule of Elranatamab during Follow-up Period for Patients Switching to

Q2W and Table 11. Dosing Schedule of Elranatamab during Follow-up Period for Patients staying on

QW Table 10. Dosing Schedule of Elranatamab during Follow-up Period for Patients Switching to

Q2W).

$$\text{RAI} = \frac{\text{Number of administrations received}}{\text{Number of expected administrations during the time period}}$$

a) Schedule 1¹

Assumption that all patients switch to bi-weekly doses (Q2W) after day 169 post-index.

Table 10. Dosing Schedule of Elranatamab during Follow-up Period for Patients Switching to Q2W

Follow-up Sub-Periods	Expected Administrations	Vial Size
Index date - Day 8	3 administrations	2 x 44mg/1.1mL 1 x 76mg/1.9mL
Day 9 - Day 168	1 administration per week	76mg/1.9mL
Day 169 – End of follow-up	1 administration every two weeks	76mg/1.9mL

Notes:

090177e1a4a71ff1\Approved\Approved On: 05-Nov-2025 14:15 (GMT)

¹ Adapted from dosing and administration guidance of the Japanese elranatamab label available at <https://labeling.pfizer.com/ShowLabeling.aspx?id=20462>

b) Schedule 2¹

Assumption that all patients continue with weekly doses (QW) after day 169 post-index.

Table 11. Dosing Schedule of Elranatamab during Follow-up Period for Patients staying on QW

Follow-up Sub-Periods	Expected Administrations	Vial Size
Index date - Day 8	3 administrations	2 x 44mg/1.1mL 1 x 76mg/1.9mL
Day 9 – End of follow-up	1 administration per week	76mg/1.9mL

Notes:

¹ Adapted from dosing and administration guidance of the Japanese elranatamab label available at <https://labeling.pfizer.com/ShowLabeling.aspx?id=20462>

Treatment exposure will be assessed across the different follow-up periods. End of follow-up is defined as the end of the hospital claim of the last elranatamab administration inclusive.

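### Patient-level duration of treatment (Table 4) is summarised without separating patients who stopped elranatamab from those still on it at the data cut, so it measures observed exposure and understates treatment duration.

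*Protocol*

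**What the plan says.** Primary Objective 2 is "To describe and characterize elranatamab utilization, including timing, administration and dosing, during the follow-up period". Table 4, under the heading Covariates and Outcomes, lists patient-level duration of treatment for that objective and defines it as "Days between first and last treatment administration for elranatamab (continuous", assessed over the follow-up period.

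The summary method is fixed in section 9.7.1: "Continuous variables will be described using mean, standard deviation (SD), median, interquartile range (IQR), minimum, and maximum".

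Three other statements determine what that summary measures:

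- Section 9.7.3, in line with sections 9.1 and 9.2: "End of follow-up is defined as the end of the hospital claim of the last elranatamab administration inclusive".
- Section 9.1 takes adults who "initiated elranatamab between March 26, 2024, the PMDA approval date for elranatamab, and the end of data availability". The inclusion criteria in section 9.2.1 set no minimum follow-up.
- Section 9.5: "The most recent data cut available from MDV will be used for the report". Section 6 dates the interim analysis 30 September 2025, and the abstract says: "Data collection will conclude on June 30, 2026".

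The protocol has no rule for ongoing patients and does not ask for a count of them. Section 9.7.6 excludes sensitivity analyses. Section 9.9 mentions facility transfers and data lag, but not truncation of duration at the cut. The claim-level duration row in Table 4 reports total calendar observation, which gives context but corrects nothing.

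**The concern.** For a patient who has stopped, the days from first to last dose are the treatment duration. For a patient dosed shortly before the cut, the same calculation gives only a lower bound. The plan pools both kinds of value as if complete and takes their mean and median. Because entry continues to the end of the data, the most recent starters necessarily contribute short values, however long they will in fact be treated.

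Two things are at stake. First, a figure labelled as duration of treatment under a primary objective will be read as how long patients stay on the drug, and it will be too short. Second, section 12 plans external dissemination of both interim and final results. The later cut gives every earlier starter more time to accrue duration, so the reported median will rise between the two even if persistence is unchanged.

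**Working it through.** **Inputs from the protocol.** Entry opens on 26 March 2024. The two planned time points are 30 September 2025 (interim analysis) and 30 June 2026 (end of data collection). These give windows of W = 553 days (365 + 188) and W = 826 days (730 + 96), or 18.2 and 27.1 months at 30.4375 days per month. The actual cuts can only be on or before these dates. An earlier cut makes the understatement larger.

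**Assumptions.** The protocol states no duration figure, so there is nothing to reproduce. I assume true median time on treatment m of 3, 6 or 12 months (91.3, 182.6, 365.25 days), exponential discontinuation, and uniform entry over the window. The last dose is taken as the moment of stopping or the cut, ignoring the days between doses.

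**Formulas.** With T the true time on treatment and C the time from start to cut, the plan summarises min(T, C).

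- Share still on treatment at the cut: (1 − e^(−λW)) / (λW), with λ = ln 2 / m.
- Reported median t solves (1 − t/W) × 2^(−t/m) = 0.5.

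**Example**, m = 12 months, W = 826. λW = 0.6931 × 826 / 365.25 = 1.5675, so the share ongoing is (1 − 0.2086) / 1.5675 = 50.5%. At t = 210 days, (1 − 210/826) × 2^(−210/365.25) = 0.746 × 0.671 = 0.50, so the reported median is 210 / 30.4375 = 6.9 months.

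| True median | Cut 30 Sep 2025: ongoing | Reported median | Error | Cut 30 Jun 2026: ongoing | Reported median | Error |
|---|---|---|---|---|---|---|
| 3 months | 23.5% | 73 d (2.4 mo) | −20% | 15.9% | 78 d (2.6 mo) | −14% |
| 6 months | 41.8% | 119 d (3.9 mo) | −35% | 30.5% | 135.5 d (4.5 mo) | −26% |
| 12 months | 61.9% | 171 d (5.6 mo) | −53% | 50.5% | 210 d (6.9 mo) | −42% |

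A simulation of 400,000 patients per scenario gave the same figures to within a day or so. In it, the mean at the June 2026 cut was low by 16%, 30% and 51%. A Kaplan-Meier median that censors patients still on treatment at the cut returned 91, 183 and 364 days, against true values of 91, 183 and 365.

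**Entry pattern**, m = 12 months, W = 826. If starts decline linearly to zero over the window, the first factor becomes 1 − (t/W)² and the reported median is 294 days (9.7 months). If starts rise linearly from zero, it becomes (1 − t/W)² and the reported median is 152 days (5.0 months). The size changes; the direction does not.

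**The case against.** The strongest reply is that Objective 2 concerns utilization during the follow-up period, and follow-up is defined to end at the last claim. First-to-last days is then a coherent description of observed exposure. No section names persistence or time to discontinuation as an endpoint, and none says that ongoing patients have finished. This stands: the number is not wrong as observed exposure. The fault is that it is labelled duration of treatment, without that qualification and without a count of ongoing patients.

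A second reply is that discontinuation gaps and censoring dates belong in the SAP. Their absence from the protocol is indeed no finding. But the protocol itself fixes the variable as continuous and prescribes the summaries. Section 9.7 also says that major changes to primary endpoint definitions or their analyses would go into a protocol amendment. So the correction belongs in this document.

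A reader might infer that the reported figure reflects calendar time since approval and says nothing about persistence. The calculation does not support that: at the June 2026 cut it runs 2.6, 4.5 and 6.9 months for true medians of 3, 6 and 12, so it is attenuated but still tracks the truth. A reader might also apply the February 2025 cut, where truncation would be worse. Section 9.5 cites that cut only to indicate sample size, and no analysis is planned on it.

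Time to first infection (Table 8, "Time in days from index date to first infection (continuous") invites the same criticism, since short follow-up can contribute only early infections. No size has been established for it, infections are also reported as incidence and prevalence and by sub-period, and a competing-risk analysis would need follow-up to be redefined. It remains a secondary point.

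**Conclusion.** The concern holds in a limited form. Followed exactly, the plan yields a summary under a primary objective that is valid as observed exposure to the data cut and understates treatment duration. No other section corrects this.

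The direction is certain as long as some patients are on treatment at the cut. The size is not: it depends wholly on assumed durations and entry pattern. For true medians of 3 to 12 months and uniform entry, the median is low by 20% to 53% at a September 2025 cut and by 14% to 42% at a June 2026 cut. The mild end, 2.6 months reported for a true 3, would matter little. With a true median of 12 months, the reported median would move from 5.6 to 6.9 months between the two dates with no change in persistence.

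The study is descriptive, with no hypotheses or group comparisons, so this is a should-fix and not a bar to the study.

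**What to change.** In Table 4 and section 9.7.1:

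1. Add time to discontinuation by Kaplan-Meier with 95% CI. The event is one pre-specified gap without an elranatamab claim, dated at the last dose, or death.
2. Censor at the last dose those patients whose last dose falls within that gap of the data end.
3. Report the number still on treatment at the cut.
4. Keep the present summary, relabelled as observed exposure to data cut.
5. In Table 8, state that time to first infection is computed only among patients with an infection during follow-up.

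The cost is a standard procedure on the same data, with three downsides to name:

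- The gap is an analytic choice. Vary it to show robustness; this needs an exception to section 9.7.6.
- MDV follows patients within one facility (section 9.9), so a transfer out can look like discontinuation. Section 9.9 should say so.
- With censoring at the last dose, ongoing patients count as at risk during the final gap, when no gap-defined event can yet be recorded, so the curve is lifted somewhat. Under the assumptions above, with a 60-day gap taken purely for illustration and a June 2026 cut, simulated medians were 99, 199 and 407 days for true 91, 183 and 365. That is 8% to 11% high, against 14% to 42% low for the present summary. A companion run that ends everyone's observation one gap before the data end gave 91, 183 and 366 days and is worth showing alongside.

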SUD period: defined as the period between a patient's first 44mg/1.1mL vial of elranatamab and first 76mg/1.9mL vial of elranatamab, inclusive. See Section 9.3.1 and Annex 1 for more details. Within the SUD period, three sub-periods are identified:

- **Overall:** defined as the period between first 44mg/1.1mL vial and first 76mg/1.9mL vial of elranatamab.
- **First 44mg/1.1mL vial – Second 44mg/1.1mL vial:** defined as the period between the two 44mg/1.1mL vials of elranatamab, if second 44mg/1.1mL vial is administered.
- **Second 44mg/1.1mL vial – first 76mg/1.9mL vial:** defined as the period between the second 44mg/1.1mL vial and the first 76mg/1.9mL vial of elranatamab, if second 44mg/1.1mL vial is administered.

Follow-up period: defined as the period between the first hospital claim for elranatamab (index date) and the end of the hospital claim of the last elranatamab administration. Within this follow-up period, five sub-periods are identified (when sufficient follow-up time is available at the patient level). These sub-periods allow for reporting study endpoints across different phases of the follow-up period, and are based on expected dosing administrations and schedule of patients with switch to bi-weekly administrations from label guidance (see [Table 10. Dosing Schedule of Elranatamab during Follow-up Period for Patients Switching to](#)

[Q2W](#) and [Table 11. Dosing Schedule of Elranatamab during Follow-up Period for Patients staying on QW](#)):

- **Index date to day 8:** defined as the first 8 days post-index date, inclusive. Also defined as day 1 to day 8.
- **Day 9 to day 168:** defined as the period from day 9 to day 168 post-index date.
- **Day 169+:** defined as the period from day 169 post-index date to end of follow-up period.

- **Overall follow-up:** defined as the period from index date to end of follow-up period.

IVIG follow-up assessment period: defined as the 30-day window post index date. If a patient has fewer than 30 days of data available post to the index date, the assessment window will be equal to the maximum number of days available post to the index date.

CRS/ICANS follow-up assessment period: defined as the 14-day window post index date. If a patient has fewer than 14 days of data available post to the index date, the assessment window will be equal to the maximum number of days available post to the index date.

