			Number of top 5 department visits claims PPPM Note that the top 5 will not be established a priori, but rather will be determined based on the data and sample	HCRU baseline period Follow-up period (overall only)
			Number of top 5 department visits claims PPPD Note that the top 5 will not be established a priori, but rather will be determined based on the data and sample	SUD period

090177e1a4a71ff1\Approved\Approved On: 05-Nov-2025 14:15 (GMT)

Variable	Role	Data Source	Operational Definition	
			Definition	Assessment Period(s)
Degree of nursing	Outcome	MDV	Highest degree of nursing recorded (categorical), N (%) For the following categories: No support, Support level 1, Support level 2, Care level 1, Care level 2, Care level 3, Care level 4, Care level 5, Is applying, Unknown	HCRU baseline period SUD period Follow-up period (overall only)

Abbreviations: ED: emergency department; HCRU: healthcare resource utilization; IP: inpatient; OP: outpatient; PPPD: per patient per day; PPPM: per patient per month; SUD: step-up dosing.

Table 6. Variables for Outcomes (Objective 4 - Other MM treatments including supportive therapy)

Variable	Role	Data Source	Operational Definition	
			Definition	Assessment Period(s)
PIs	Outcome	MDV	Health claim code for bortezomib, carfilzomib, or ixazomib (Yes/No) Health claim code for each PI will also be reported.	Follow-up period
IMiDs	Outcome	MDV	Health claim code for lenalidomide, thalidomide, or pomalidomide (Yes/No) Health claim code for each IMiD will also be reported.	Follow-up period
anti-CD38s	Outcome	MDV	Health claim code for daratumumab, or isatuximab (Yes/No)	Follow-up period

Variable	Role	Data Source	Operational Definition	
			Definition	Assessment Period(s)
			Health claim code for each anti-CD38 will also be reported.	
SCT	Outcome	MDV	Health claim code for SCT (Yes/No) Health claim code for each SCT (allogeneic and autologous) will be reported.	Follow-up period
CAR-T	Outcome	MDV	Health claim code for idecabtagene vicleucel or ciltacabtagene autoleucel (Yes/No) Health claim code for each CAR-T will be reported.	Follow-up period
Chemotherapies	Outcome	MDV	Health claim code for chemotherapies (doxorubicin hydrochloride, melphalan, bendamustine, cyclophosphamide, etoposide, or cisplatin) (Yes/No) Health claim code for each chemotherapy will also be reported.	Follow-up period
IVIG	Outcome	MDV	Health claim code for IVIG (Yes/No)	Follow-up period

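### Treatment duration and the follow-up window run from first to last elranatamab claim with no gap rule, so for patients who stop and restart the off-drug time counts as treatment duration

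*Protocol*

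**What the plan says.** Three definitions in the protocol share the same end point.

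- **Duration (Table 4, Objective 2).** At patient level it is "Days between first and last treatment administration for elranatamab (continuous". At claim level it is "Total calendar duration of elranatamb observation in days, and the date of the first observed elrantatamab claim".
- **Follow-up (section 9.2).** It is "the period between the first hospital claim for elranatamab (index date) and the end of the hospital claim of the last elranatamab administration".
- **RAI (section 9.7.3).** "RAI will be calculated as the cumulative frequency of administration received over the expected number of administrations". Expected administrations accrue weekly, or every two weeks in the last sub-period of Schedule 1, until the end of follow-up: "End of follow-up is defined as the end of the hospital claim of the last elranatamab administration inclusive".

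Table 6 (Objective 4) counts other myeloma treatments in the same follow-up window, for example "Health claim code for idecabtagene vicleucel or ciltacabtagene autoleucel (Yes/No". Such a claim does not end or split the elranatamab course. The protocol gives no permissible gap, discontinuation rule or restart rule, and section 9.7.6 plans no sensitivity analysis.

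**The concern.** First-to-last span equals time on treatment only if dosing is uninterrupted. If a patient stops, goes months without elranatamab and then has one further claim, that claim turns a short course into a long one. This is separate from censoring at the data cut, because it affects patients whose course is fully observed.

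Duration and RAI are outputs of a primary objective. Under these definitions a restarter has a long duration with a low RAI, which is also what a patient with many scattered delays would show. The follow-up window carries the gap into Objectives 3 and 6 as well: resource use, costs and infections arising off drug, possibly under another therapy, are pooled with those arising on drug.

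**Working it through.** The study is descriptive and states no figure for duration or RAI, so there is nothing to reproduce. The check applies the protocol's own definitions to constructed patients. The dosing patterns and gap lengths are assumptions, because the protocol gives no frequency or length of interruptions.

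**Inputs from the protocol.** Tables 10 and 11 expect 3 administrations from index to day 8, then one per week. In Schedule 1 this becomes one every two weeks from day 169. Duration is last minus first administration day. RAI is received divided by expected up to the last claim.

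**Patient 1 (assumed): on schedule to day 169, 180 days without elranatamab, then doses on days 349, 356, 363 and 370.**

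- Received: 3 + (169 − 8)/7 = 3 + 23 = 26, plus 4, gives 30.
- Duration as defined: 370 − 1 = 369 days.
- Time within the two courses: (169 − 1) + (370 − 349) = 168 + 21 = 189 days. Ratio 369/189 = 1.95.
- Schedule 2 expected: 3 + (370 − 8)/7 = 54.7. RAI = 30/54.7 = 0.55.
- Schedule 1 expected: 3 + 160/7 + 202/14 = 40.3. RAI = 30/40.3 = 0.74.
- First course only, Schedule 2: expected 3 + 161/7 = 26. RAI = 26/26 = 1.00.
- Gap as a share of the span: 180/369 = 49%.

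By sub-period the same patient has:

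| Sub-period | Received | Expected | RAI |
|---|---|---|---|
| Day 1-8 | 3 | 3 | 1.00 |
| Day 9-168 | 22 | 160/7 = 22.9 | 0.96 |
| Day 169+, Schedule 1 | 5 | 202/14 = 14.4 | 0.35 |
| Day 169+, Schedule 2 | 5 | 202/7 = 28.9 | 0.17 |

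**Patient 2 (assumed): 3 administrations by day 8, weekly to day 85, a gap, then 8 weekly administrations.** Received 3 + 11 + 8 = 22. Time within the two courses is 84 + 49 = 133 days whatever the gap. Expected administrations are counted here as scheduled dose days.

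| Gap (days) | Duration as defined | RAI, Schedule 1 | RAI, Schedule 2 |
|---|---|---|---|
| 14 | 147 | 22/23 = 0.96 | 22/23 = 0.96 |
| 60 | 193 | 22/27 = 0.81 | 22/29 = 0.76 |
| 90 | 223 | 22/29 = 0.76 | 22/33 = 0.67 |
| 120 | 253 | 22/32 = 0.69 | 22/38 = 0.58 |
| 180 | 313 | 22/36 = 0.61 | 22/46 = 0.48 |

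Duration is 1.1 (147/133) to 2.35 (313/133) times the time within the courses.

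**Cohort mean.** The rise in mean duration is the share restarting times the gap.

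- 180-day gap: 2% gives 0.02 × 180 = 3.6 days; 10% gives 18 days. Of the 128 patients in section 9.5 these shares are about 3 and 13 people.
- 120-day gap: 5% gives 6 days, 10% gives 12, 20% gives 24.

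**The case against.** **It is a transparent definition, and the SAP may refine it.** First-to-last span is used consistently, and section 9.7 sends detailed methods to the SAP, which may add a gap rule. That limits the point but does not remove it. The protocol has already fixed the definition, and the same section says that major changes to primary endpoint definitions would go into an amendment.

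**RAI is doing its job.** A reader might infer that RAI treats restarters as continuously treated. It does not: a gap lowers RAI, because expected administrations accrue while none are received. What stands is that one low value cannot distinguish delay from stopping and restarting. Restricting RAI to the first episode alone would remove long delays that RAI is meant to show, so that should not replace the full-span figure.

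**Other outputs expose part of the gap.** This stands. Sub-period RAI for patient 1 is near full to day 168, and the loss sits in day 169+. Inter-claim intervals are reported, and a maximum at claim level would show a 180-day gap. Neither output counts restarters or corrects duration, and a patient's mean interval blends one long gap with many short ones.

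**Attribution.** A reader might infer that infections in the gap are reported as associated with elranatamab use. That wording belongs to Objective 3 on resource use and costs; Objective 6 only describes infections during follow-up. Resource use is labelled all-cause, and per-month rates carry the gap in the denominator too, so the direction of any cost distortion is not fixed.

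**Table 6 as evidence.** It is tempting to read Table 6 as proof that the plan expects other therapy between elranatamab claims. Its yes/no items could equally record concomitant use. No objective names restart or retreatment.

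**The size is hypothetical.** This stands too. The 128 patients come from the February 2025 cut, at most about 340 days after 26 March 2024, so patient 1 (day 370) could not yet appear there, although patient 2 with a 120-day gap (day 254) could. Data collection to 30 June 2026 allows about 27 months.

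**Conclusion.** The point holds as a limitation of stated definitions. For any patient who stops and restarts, off-drug time is reported as duration of treatment, RAI mixes two different patterns, and all-cause resource use, costs and infections in the gap fall inside follow-up.

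For an individual the effect can be large (369 against 189 days in patient 1). For the cohort it depends on the share of restarters, which the protocol does not give. Assuming 2-10% with a 180-day gap, mean duration rises by about 4-18 days and the median by less; with no restarters there is no effect. The change is worth making because duration and RAI serve a primary objective and the remedy is cheap. The protocol does not support saying that RAI makes restarters look continuously treated, or that infections in the gap are attributed to elranatamab.

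**What to change.** In section 9.2, Table 4 and section 9.7.3:

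1. Keep the first-to-last measure but label it as elapsed span.
2. Add an on-treatment duration. End the first episode at the last administration before either a pre-specified elranatamab-free gap (for example 90 days, repeated at 60) or a CAR-T or SCT claim, whichever comes first.
3. Report the number of patients who restart and the distribution of gap lengths.
4. Show RAI over the full span and within the first episode, side by side.
5. For Objectives 3 and 6, tabulate follow-up resource use, costs and infections in the gap separately from those on treatment.

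This is an analysis rule only and says nothing on how patients should be treated. The cost is some wording, one episode-building step on claims already extracted, and a few extra table columns. The downside is that the gap length is a convention, which showing two values makes visible. A switch to another drug class within a gap shorter than the cut-off would remain unsplit, and the report should say so.
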